### Studyprotocol, v.1.3 20.12.2024

Changes in muscle strength	

○ Isometric muscle strength

	Dynamometry for handgrip strength (HGS)
Changes in muscle function	

○ Muscle power

○ Gait speed

	30sSTS 5 x STS 10 m. walking test (maximal and habitual)
Geriatric treatment-related vulnerability	

○ Geriatric-8 screening tool

	Filling in of the G8 will be partly self-reported by the patient and from medical records.
Frailty	

○ Clinical Frailty Scale (CFS)

	Assessed at visit at hospital by physician or investigator
Vulnerability index	

○ Items for new scale to predict treatment adherence

	Self-reported items on social vulnerability and obtained from medical records

A comprehensive health/capacity assessment will be completed by an investigator (physiotherapist or exercise physiologist) before every test session and include the following: (a) exercise preparticipation health screening, and pre-exercise evaluation; (b) measurement of body composition by bioimpedance analysis; (c) measurement of maximal muscle strength by HGS using a hand dynamometer (Jamar); (d) muscular function; firstly, lower-extremity muscular function by 30-second sit to stand test (30sSTS). Concurrently, five times stand up within the 30sSTS test will be measured using an additional stopwatch. Secondly, maximal and habitual gait speed will be measured over a 10-meter straight walking course. In-depth descriptions of the testing procedures can be found in (Appendiks 2a testmanual på dansk).

#### 5.5.2 Questionaries

##### **Treatment-related vulnerability**

A tool commonly used to identify prognostic vulnerability among older patients with cancer is the Geriatric-8 screening tool (G8) originally developed from the Mini Nutritional Assessment questionnaire. The G8 is recommended by the International Society of Geriatric Oncology (SIOG) and was originally designed to identify older patients who would benefit from geriatric assessment and intervention in the trajectory of cancer treatment. Studies have found that the G8 has high sensitivity and negative predictive value in identifying older patients at risk of negative outcomes when undergoing surgery for cancer. Patients with a score of  $\leq 14$  will be regarded vulnerable regarding treatment, while patients with a score of  $\geq 15$  will be regarded “fit”. Filling in of the G8 will be partly self-reported by patient and from medical records.

### **Self-reported physical activity levels**

Participants will be asked about their self-reported weekly physical activity, moderate-to-vigorous physical activity and daily sedentary time using single-item questions.

### **Health-Related Quality of Life**

HRQOL, evaluated by self-reported questionnaires, is a valid and strong measure. It correlates with various crucial aspects such as longevity, health habits, mental and physical well-being, social connections, and productivity among cancer patients. The European Organization for Research and Treatment of Cancer Quality of Life Questionnaire (EORTC QLQ-C30) is an integrated system for assessing the HRQoL of cancer patients participating in clinical studies and other types of research in which patient-reported outcomes are collected. The EORTC QLQ-C30 is designed for use in a wide range of cancer populations and is intended to be supplemented by tumour-specific questionnaire modules such as those for lung cancer (QLQ-LC13).

HRQoL will be evaluated by EORTC QLQ-C30 and EORTC QLQ LC13. Items from EORTC-QLQ-C30 contain a global scale covering global Quality of Life (QoL), five functioning scales and 9 symptoms scales. Items from the EORTC QLQ LC13 contain ten disease-specific symptom scales.

All the scales and single-item measures range in score from 0 to 100. Thus, a high score for the global health status / QoL represents a high QoL, a high score for a functional scale represents a high / healthy level of functioning, but a high score for a symptom scale / item represents a high level of symptomatology / problems.

### **Social vulnerability index**

We have based on knowledge from previous studies and feedback from clinical experts and patients on factors impacting treatment adherence among lung cancer patients, developed and pilot tested a vulnerability instrument to predict adherence to treatment. The instrument include nine clinical and patient-reported vulnerability criteria: (1) stage (from medical journal), (2) comorbidity (somatic or psychiatric) (from medical journal), (3) age (from medical journal), (4) performance status (from medical journal), (5) activities of daily living (three patient-reported items regarding difficulties with personal hygiene, taking a walk and climbing stairs), (6) social support (three patient-reported items

Appendiks 2  
Studyprotocol, v.1.3 20.12.2024

regarding emotional support as well as support with practicalities at home and transportation), (7) health literacy (three patient-reported items regarding difficulties in understanding healthcare information, instructions from healthcare professionals and filling in forms), (8) transportation related barriers for treatment (three patient-reported items regarding difficulties in reaching the hospital due to lack of transportation, long distance to the hospital or limited energy) or (9) alcohol abuse (three patient-reported items regarding alcohol consumption) 

**Table 2 – Self-reported questionnaires**

Patient characteristics and Exploratory outcomes	Scale, Reference	Abbreviation	Details
Sociodemographic factors	Education, work market affiliation, civil status, cohabitation status	Self-constructed	Items: 4 (only at baseline)
Weight, clinical characteristics and smoking	Current weight and 12+6 month(s) ago	Self-constructed and 3 self-reported G8 items	Items: 9 (only at baseline)
Vulnerability index	Items for new scale to predict treatment adherence	New scale that will be validated in this study	Items: 15 (only at baseline)
Physical activity levels	Physical activity levels	Self-constructed	Items: 3 (only at baseline)
Health-Related Quality of Life (Functioning and symptoms)	The European Organization for Research and Treatment of Cancer Quality of Life Questionnaire	EORTC QLQ-C30	Items: 30 Domains: 15
Health-Related Quality of Life (Disease-specific symptoms)	The European Organization for Research and Treatment of Cancer Quality of Life Questionnaire Lung cancer module: QLQ-LC13	EORTC QLQ-LC13	Items: 13 Domains: 10

Participants will be asked to fill out a questionnaire comprising different scales and self-constructed questions addressing exploratory outcomes and additional information, possible mediators and confounders (Table 2) at diagnosis, after 3 months and after 6 months. The questions will be gathered to comprise one extended questionnaire. Weight and clinical characteristics and socio-demographic factors will only be collected at baseline.

Patients can complete the questionnaire on paper on the first test day if there is enough time and a quiet space available. Further, patients can complete it at home, where they will receive the

## Appendiks 2

### Studyprotocol, v.1.3 20.12.2024

questionnaire electronically. If the patient prefers to fill out the questionnaire at home, and lack necessary electronic skills, it can be done over a phone call, where a project staff member assists the patient through the questions verbally. It will be agreed with the patient when and how it would be most convenient for them, but the first questionnaire must be completed before the treatment initiation or as soon as possible thereafter (at the latest, one week after the start of treatment). Data collections will be managed through REDCap.

## 5.6 Data collection timeline

**Table 3**

Months (number)	1	2	3	4	5	6	12
Test/Examination							
Muscle mass by routine CT-scans*	•		•			•	•
Muscle mass by bioimpedance analysis	•		•			•	
Muscle strength tests	•	•	•	•	•	•	
Muscle function tests**	•	•	•	•	•	•	
Frailty	•		•			•	
Questionnaires							
Self-constructed G8 items	•						
Social vulnerability instrument	•						
Lifestyle	•						
EORTC-QLQC30, EORTC-QLQLC13	•		•			•	

\*Up to 12-months.

Routine CT scans are generally performed at defined intervals during the diagnostic and treatment course, typically at diagnosis, around 3 months, and at 6 months. For our analysis, we aim to utilize the most recent CT scan conducted within 12 months as the post-treatment measure to evaluate changes in muscle mass before and after treatment. If the final CT scan post-treatment occurs earlier, for instance, at 4.5 or 9 months, this scan will be used as the endpoint measure. It is important to note that no additional CT scans beyond routine scans and the established 12-month timeline will be scheduled.

\*\*3 muscle function tests as presented in Table 1

Abbreviations; Computed Tomography (CT); The European Organization for Research and Treatment of Cancer Quality of Life Questionnaire (EORTC-QLQC30), and lung cancer module (EORTC-QLQLC13).

## 6.0 Statistics

### 6.1 Power considerations and statistical analysis

The population size (n=180) is calculated based on a pooled estimate from prospective cohorts, including patients with advanced stage lung cancer, with a hazard ratio for mortality risk of 2.38 and a prevalence of sarcopenia for the population of 50%. With power set to 90% and alpha=0,05, we

## Appendiks 2

### Studyprotocol, v.1.3 20.12.2024

have to include 130 patients with advanced stage lung cancer. To account for an expected study withdrawal rate of approximately 28%, we need to ensure that we have 130 patients remaining by the end of the study. To find the initial number of participants required, we divide the final required sample size (n=130) by the retention rate (0.72). Rounded up to the nearest whole number, we need to include 180 patients with advanced stage lung cancer. Our recruitment method (at time of referral for suspicion of lung cancer) will include non-cancer patients, patients at low stage who undergo surgery, which means the total cohort will include n=500 participants, to ensure 180 patients with advanced stage lung cancer. This total cohort will enable subgroup analyses comparing cancer and non-cancer participants, as well as analyses within different treatment subgroups.

We will stratify analyses according to relevant categories in uni- and multivariate regression analyses examine associations between exposures and outcomes, presenting estimates of regression coefficients and odds ratios with 95% confidence intervals and p-values and use mixed effect models for repeated measurements.

For the social vulnerability screening instrument, we will describe the distribution of each factor included in the vulnerability screening tool. Next, we will use statistical analysis ('prediction models') to select the vulnerability factor that best predicts treatment adherence (measured in Relative Dose Intensity). Furthermore, we will examine the sensitivity and specificity of the screening tool using different cut-off scores to assess the optimal cut-off for identifying patients who did not completed treatment optimally.

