## 4.0 Aims

The overall aims of the PHILUCA study are in a longitudinal study to examine sarcopenia and cachexia risk factors, the development over time, and the associations with lung cancer treatment tolerance, QoL and prognosis. In addition, the aim is to test whether a vulnerability screening tool can identify patients at high risk of not completing the planned treatment.

## Appendiks 2

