### Studyprotocol, v.1.3 20.12.2024

#### 4.1 Research Question and hypothesis

What is the prevalence and pattern of development of sarcopenia and cachexia and what are the associated factors, prognosis, treatment tolerance and QoL throughout treatment?

We hypothesize that if the Danish stage distribution of sarcopenia and cachexia is worse than that of other countries - and health is worse than that of other countries, then the risk of sarcopenia and cachexia might also be higher and could explain why we have a relatively larger subgroup of patients with lung cancer who have low 1-year survival rates.

Which patient-related and disease-related factors from can best predict treatment adherence as part of a vulnerability screening instrument?

We hypothesize that selected patient-related and disease-related factors can contribute to a vulnerability scale and that this scale is able to predict treatment adherence.

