### Studyprotocol, v.1.3 20.12.2024

## 5.3 Population

### 5.3.1 Inclusion criteria

- Patients newly diagnosed with histologically verified lung cancer and scheduled for oncological treatment
- Age > 18 years
- Expected survival > 3 months

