### 5.5.1 Measurements and clinical data

**Table 1** shows the outcomes, measurements and sources that will be used in the study period.

Endpoints	Description	Test/sample/source
Primary outcome		
Survival	
 
○ 1-year overall survival
 
○ 5-year overall survival
 
	Medical records Medical records
Exploratory outcomes		
Sarcopenia	
 
○ Muscle strength and mass and change over time
 
	Routine CT-scan (baseline CT to last performed CT within 12-months after diagnosis) & bioimpedance analysis
Cachexia	
 
○ Stages of cachexia and change over time
 
	Muscle mass (by routine CT-scan and bioimpedance analysis), abnormal biochemistry by routine blood samples and weight loss
Chemotherapy completion rate	
 
○ Mean RDI in %
 
○ Number of patients with an RDI < and <math>\geq 85\%</math>
 
○ Dose-limiting toxicity (DLT) DLT defined as 'switching treatment', 'treatment delay' (<math>\geq 3</math> days from initially planned), 'treatment de-escalation' (dose reduction <math>\geq 15\%</math> of platinum agent), early treatment termination, and hospitalization <math>\geq 1</math> day, all due to chemotherapy-induced side effects.
 
	Medical records
Treatment complications	
 
○ Complications related to surgery, radiotherapy, immunotherapy and targeted therapy.
 
	Medical records
Biomarkers	
 
○ Routine blood tests of plasma CRP and serum-albumin to diagnose cachexia and haematological toxicities
 
	Medical records
Changes in body composition	
 
○ Total muscle and fat mass
 
	Routine CT-scans Bioimpedance analysis

## Appendiks 2

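### Section 6.1 measures treatment adherence by relative dose intensity, so chemotherapy ended by progression or death counts as non-adherence unless reasons are separated

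*Protocol*

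**What the plan says.** The protocol describes the target of the vulnerability tool in two ways. Section 4.0 aims to "test whether a vulnerability screening tool can identify patients at high risk of not completing the planned treatment". Section 4.1 hypothesizes that "this scale is able to predict treatment adherence".

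Section 6.1 makes RDI the measure of adherence for choosing predictors: the analysis will "select the vulnerability factor that best predicts treatment adherence (measured in Relative Dose Intensity"). It then varies the tool's score to "assess the optimal cut-off for identifying patients who did not completed treatment optimally".

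Table 1 (section 5.5.1) has one row on chemotherapy completion with three entries: mean RDI, the number of patients below and at or above 85%, and dose-limiting toxicity (DLT). Only the DLT entry is restricted by cause, to events "all due to chemotherapy-induced side effects". The RDI entries carry no such restriction, and no denominator is given.

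The tool itself (section 5.5.2) rests on "nine clinical and patient-reported vulnerability criteria: (1) stage (from medical journal"), followed by comorbidity, age, performance status, daily activities, social support, health literacy, transport barriers and alcohol.

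**The concern.** RDI records how much of the chemotherapy was given, not why the rest was withheld. A shortfall can come from toxicity, refusal, difficulty in reaching the hospital, progression or death. Only some of these are failures of adherence or tolerance.

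This matters because section 6.1 uses RDI to choose among predictors. The tool mixes markers of prognosis (stage, age, performance status) with social items (support, health literacy, transport). If stops for progression or death count as non-adherence, the prognostic items may be favoured for reasons unrelated to adherence, and the social items may look weaker than they are.

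The sarcopenia analyses face a similar question. Section 7.1 says that the record data serve to study how muscle measures relate to treatment tolerance. The sample size assumes a mortality hazard ratio of 2.38 for sarcopenia. An association between sarcopenia and low RDI could therefore partly repeat the survival association.

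**Working it through.** The protocol gives no figure on this point to reproduce. The check sets the sections side by side and adds two illustrations whose inputs are assumptions.

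**Which denominator the text suggests.** Table 1 places RDI under chemotherapy completion, and section 4.0 speaks of completing planned treatment. Both point to the planned course as the reference.

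**What RDI then does with an early stop.** For a patient given full, on-time doses for k of K planned cycles, RDI = k/K. The values of K are assumed; the protocol gives no course length.

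- K = 4: 1/4 = 25%, 2/4 = 50%, 3/4 = 75%
- K = 6: 5/6 = 83.3%

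Each value is below the 85% line in Table 1 and is the same whatever the reason for stopping.

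**What mixing the reasons does to the tool's apparent sensitivity.** Let Se be the true sensitivity for patients with low RDI for reasons of tolerance or adherence. Let q be the share of low-RDI patients who stopped for progression or death, and f the proportion of those whom the tool flags. Then

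apparent sensitivity = (1 − q) × Se + q × f.

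Assume Se = 0.80 and specificity 0.70.

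- If the tool flags these patients only at the background rate, f = 1 − 0.70 = 0.30. For q = 0.2: 0.8 × 0.80 + 0.2 × 0.30 = 0.70. For q = 0.4: 0.6 × 0.80 + 0.4 × 0.30 = 0.60. For q = 0.6: 0.4 × 0.80 + 0.6 × 0.30 = 0.50.
- If stage and performance status make the tool flag them often, say f = 0.90, then for q = 0.4: 0.6 × 0.80 + 0.4 × 0.90 = 0.84.

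The effect can go either way, depending on whether f is below or above Se. The protocol gives neither q nor f.

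**Whether the reason will be on file.** Section 7.1 lists the degree of treatment completion and complications among the record data, but not the reason for stopping. Scoring DLT requires a judgement whether side effects caused an event. It does not require progression, death, patient choice and logistics to be told apart.

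**The case against.** The strongest reply is that all-cause non-completion is what the study wants. Section 4.0 sets no limit by cause, and a screening tool may properly flag anyone unlikely to finish treatment. Stage, age and performance status are deliberate items, and it is no error that they also predict disease course. This stands for the aim in section 4.0. It does not carry over to section 4.1, which claims prediction of adherence.

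Second, the same row of Table 1 already contains a toxicity-specific endpoint, DLT. This also stands: tolerance, including its relation to sarcopenia, need not be judged by RDI alone. But DLT is not the measure of adherence named in section 6.1, and it does not cover patient choice or logistics.

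Third, details of derivation may sit in a statistical analysis plan that is not shown. That is fair for the formula. The protocol itself, however, ties adherence to RDI, and a later plan can separate reasons only if they are recorded.

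A reader might infer more than the text supports:

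- That RDI could be taken over delivered cycles, so that a patient stopped by toxicity after the first cycle scores 100%. The table row and the aim point to the planned course.
- That RDI below 85% is the reference standard for the tool. Section 6.1 does not say so; the cut-offs it mentions are scores of the tool.
- That early death must be common because eligibility asks for "Expected survival > 3 months". This criterion selects against early death and gives no rate of stopping.

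**Conclusion.** The point holds as a limit on interpretation, not as an error in the plan. With RDI taken against the planned course, low RDI combines poor tolerance or adherence with progression and death. The planned analysis can support a statement about non-completion, but by itself not one about adherence.

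The documents do not support the claim that the tool's performance will be inflated. In the illustration an assumed sensitivity of 0.80 becomes 0.60 or 0.84 at q = 0.4, according to the assumed f. The course lengths, q, f, sensitivity and specificity are all assumptions, so no size or direction can be stated for this study.

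The outcomes concerned are listed as exploratory. The primary survival outcome and the sample size are unaffected. The change is a worthwhile improvement at low cost.

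**What to change.** In Table 1 and section 6.1:

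1. State that RDI is calculated against the course planned at cycle 1.
2. Abstract the reason for each early stop or reduction (toxicity, patient choice, logistics, progression, death), and add this item to the record data in section 7.1.
3. Keep all-cause RDI as the non-completion outcome for the aim in section 4.0.
4. Add an analysis of the tool's predictors, sensitivity and specificity, and of the sarcopenia–RDI models, in which low RDI due to progression or death is a separate outcome category and not non-adherence.
5. Base any claim about adherence or tolerance on that additional analysis.

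The cost is protocol wording, one more abstracted field and fewer events in the cause-specific analysis. The protocol update already reports on the first 153 included patients, so many reasons would have to be taken from the records retrospectively. Section 7.1 already provides for review of those records during treatment.

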## 7.0 Data management and storage

### 7.1 Data from medical records

Before the study recruitment, relevant clinical information will be passed to the investigators in order to identify potential patients for inclusion at the Department of Pulmonary Medicine, ZUH. Based on patient lists these will include: personal and contact information (name, address, phone number, email), date of next visit to clinic, and sensitive personal information (CPR number, suspected cancer type). During the invitation session, the exclusion criteria of severe physical or cognitive comorbidities will be assessed by asking the patient. We expect up to 10 % of approached patients will decline participation. We therefore need to screen approximately 1550 patients within the period of

## Appendiks 2

### Studyprotocol, v.1.3 20.12.2024

01.09.2024 to 01.09.2027. If patients decline participation, all information stored will be deleted immediately.

After written informed consent has been obtained from participants at baseline the medical records will be reviewed by an investigator at regular intervals during lung cancer treatment to collect data on sociodemographic characteristics, anthropometrics, health status, functional status, and clinical information on cancer type and cancer treatment. These include:

- Ordinary personal information; name, address, phone number, email, cohabitation status, employment status, age and sex.
- Sensitive personal information; CPR number, cancer type, cancer treatment, body mass index, body surface area, information on the degree of treatment completion and complications, physical or cognitive comorbidities, CT scan images, PS, time since cancer diagnosis, results from standard blood tests.

The patient's consent gives the investigator and their representative direct access to this information to conduct, monitor, and audit the study. The information from medical records is collected with the aim of investigating whether muscle mass, strength, and function are related to treatment tolerance. The medical records will be reviewed at the end of the study by one of the investigators to extract data on recurrence and survival for a period of up to 1 year and 5-years after lung cancer diagnosis. The data will be handled with confidentiality according to Part 7.2 and used for descriptive statistics of participants and in multivariate analyses of outcomes in a pseudonymised form. Participants who initially provided informed consent and had performed baseline measurements, but were later found not to have lung cancer will contribute with data for comparison analysis between people with and without lung cancer on variables such as sociodemographics, clinical characteristics, baseline physical function and body composition, and survival. No additional measurements beyond baseline testing will be conducted for this cohort. All data will be securely handled in compliance with ethical and confidentiality standards.

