### **Update to data collection timepoints**

The study protocol was amended with respect to the timing of follow-up assessments.

Due to logistical and time constraints in the clinical setting, it was not possible to assess changes in muscle parameters or health-related quality of life beyond **three months after inclusion**. Furthermore, repeated assessments of muscle parameters at each chemotherapy cycle during first-line treatment could not be performed, as these timepoints coincided with treatment administration and clinical workflows that did not allow for additional study procedures.

As a result, follow-up assessments were limited to a single post-baseline timepoint. Assessments are intended to be performed approximately **three months after inclusion**, which in routine clinical practice usually corresponds to the timepoint immediately **prior to the first control imaging scan**. This timing ensures clinical relevance while maintaining feasibility and minimizing participant burden.

These changes do not affect the primary study objectives but define the scope of longitudinal analyses accordingly.

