## 5.4 Study Procedure

### 5.4.1 Recruitment procedure

Patients with suspected lung cancer will be recruited from the Department of Pulmonary Medicine, Zealand University Hospital (ZUH), Næstved. According to reports from the Department of Pulmonary Medicine, > 70% of cases patients will be diagnosed with lung cancer, but in the approximately 30% of patients where a lung cancer diagnosis is not confirmed we omit follow-up assessments. This will thoroughly be explained to the patient verbally and in the written information leaflet during invitation.

Moreover, eligible candidates not already identified from Department of Pulmonary Medicine, will be identified during the multidisciplinary team (MDT) lung cancer conference within the Department of Clinical Oncology and Palliative Care. Subsequently, following a comprehensive medical examination during their initial outpatient visit, patients meeting the specified inclusion criteria will be approached by the attending physician regarding potential participation in the study.

It is important to emphasize that patient recruitment may occur at two distinct time points: first, during the diagnostic phase when suspicion of lung cancer arises, and second, during the initial outpatient visit at the Department of Clinical Oncology and Palliative Care after further evaluation and confirmation of eligibility criteria. This dual approach ensures a comprehensive recruitment strategy,

## Appendiks 2

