#### 5.5 Study measurements

Participation in the study involves measurements of muscle mass (body composition), muscle strength, muscle function, and patient-reported outcomes on lifestyle and social vulnerability factors (only at time of diagnosis) and QoL and frailty. All physical measurements are performed while the patient is at the hospital for treatment or examination. For patients undergoing chemotherapy, physical tests are - in addition to the planned assessments at the time of diagnosis, after 3 months, and after 6 months - also performed before each treatment cycle, but no later than 6 months after the diagnosis. A timeline of data collection is presented in part 5.6.

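### The only stated survival clock starts at lung cancer diagnosis, but patients enter on either side of that date and the non-cancer comparison group has no such date

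*Protocol*

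**What the plan says.** Table 1 (section 5.5.1) names "1-year overall survival" and its 5-year counterpart as the primary outcome and gives no time origin. The only place that fixes a start is section 7.1, where an investigator will go through the medical records at the end of the study to "extract data on recurrence and survival for a period of up to 1 year and 5-years after lung cancer diagnosis".

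On entry, section 5.4.1 says that "patient recruitment may occur at two distinct time points: first, during the diagnostic phase when suspicion of lung cancer arises". The other route opens later in the pathway, once the diagnosis has been made and the patient is seen in oncology; the same section words it as "second, during the initial outpatient visit at the Department of Clinical Oncology and Palliative Care after further evaluation and confirmation of eligibility criteria". Baseline testing follows consent (section 5.4.2).

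Section 7.1 also keeps participants who completed baseline tests and were later found not to have lung cancer. They are to be compared with the cancer patients on a list of variables that ends with "baseline physical function and body composition, and survival". Section 6.1 confirms that cancer versus non-cancer subgroup analyses are planned in the total cohort of 500.

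**The concern.** A survival clock is safe when it starts at or after the moment a person comes under observation and can be assigned to a group. Here the clock is tied to diagnosis and observation is tied to enrolment, and these dates differ in opposite directions for the two routes.

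- **Enrolled at the first oncology visit:** the patient must have lived from diagnosis to enrolment. Counting that interval as follow-up adds guaranteed survival.
- **Enrolled on suspicion:** baseline is measured before the clock starts, and the patient is classed as having lung cancer only on reaching a diagnosis.
- **Found not to have lung cancer:** the stated rule gives neither a start of follow-up nor a window for extracting survival.

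Absolute survival matters because the hypothesis in section 4.1 concerns low 1-year survival and refers to other countries. The two routes would also be counted differently within one primary outcome.

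**Working it through.** **The plan's own figures.** The protocol gives no survival proportion and no interval between diagnosis and baseline, so there is no stated figure on this point to reproduce. The sample size does not depend on the time origin: 130/0.72 = 180.6 against the stated 180, and 130/0.81 = 160.5 against 160, each within one patient. With a hazard ratio of 2.38, 50% prevalence, 90% power and two-sided alpha 0.05, the required deaths are 4(1.960 + 1.282)²/(ln 2.38)² = 56 (Schoenfeld) or 64 (Freedman). As a share of 130 these are 0.43 and 0.49. If those deaths fell within one year, 1-year survival would be 51% to 57%, inside the 40% to 60% range assumed below.

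**Setting the dates side by side.** Diagnosis starts the clock (7.1). Entry is before or after it (5.4.1). The first questionnaire is tied to neither: "the first questionnaire must be completed before the treatment initiation or as soon as possible thereafter". Section 5.5 places the first assessment at diagnosis ("in addition to the planned assessments at the time of diagnosis, after 3 months, and after 6 months"), whereas the later update counts follow-up from enrolment: "Assessments are intended to be performed approximately three months after inclusion". Because the update amends the schedule, I do not count that difference as an error. It does show that diagnosis and inclusion are separate dates.

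**Size for absolute survival, post-diagnosis route.** Assume exponential survival with true 1-year survival S and enrolment a fixed d weeks after diagnosis. Survival to one year among those alive at enrolment is S/S^(d/52) = S^(1 − d/52). For example, 0.50^(50/52) = 0.514.

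| True 1-year survival | 2 weeks | 4 weeks | 6 weeks | 8 weeks |
|---|---|---|---|---|
| 40% | 41.4% | 42.9% | 44.5% | 46.1% |
| 50% | 51.4% | 52.7% | 54.2% | 55.6% |
| 60% | 61.2% | 62.4% | 63.6% | 64.9% |

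The excess runs from 1.2 to 6.1 points and applies only to patients enrolled after diagnosis. In a simulation where half the patients entered late, the whole-cohort figure rose from 48.8% to 50.2% (4 weeks) and from 49.1% to 52.1% (8 weeks).

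**Size for the sarcopenia association.** The simulation used 12,000 patients per scenario, 50% sarcopenic, a yearly hazard of 0.45 without sarcopenia, a true hazard ratio of 2.38, follow-up cut at 1 year, and delay unrelated to sarcopenia. Cox hazard ratios ignoring delayed entry were 2.32 to 2.51 with delay and 2.36 to 2.44 without, a difference consistent with simulation noise.

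Section 6.1 names odds ratios, and a 1-year odds ratio is more sensitive. Take 1-year survival of 64% without sarcopenia, hence 0.64^2.38 = 34.6% with it. The true odds ratio for death is (0.654/0.346)/(0.36/0.64) = 3.36. Now suppose 70% of sarcopenic and 30% of other patients enter late. With a 1-month delay, survival reads as 0.7 × 0.346^(11/12) + 0.3 × 0.346 = 36.8% and 0.3 × 0.64^(11/12) + 0.7 × 0.64 = 64.7%, giving an odds ratio of 3.15. With 2 months it is 2.94. With the split reversed it is 3.48 and 3.59. The shares are assumptions, and the direction depends on who enters late.

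**Non-cancer comparison.** This needs no arithmetic. The rule requires a diagnosis date, and one of the two groups has none.

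**The case against.** The strongest reply is that the sentence in section 7.1 is a record-extraction window under data management and does not define an endpoint. Table 1 leaves the origin open, and an analysis plan could still set another origin or use delayed entry. Section 7.1 lists time since cancer diagnosis among the collected items, so the means to do so exist. This stands: bias is a risk of following the text as written, not an established fact.

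The size also has to be qualified. The delay is assumed. Section 6.1 describes recruitment as taking place at referral on suspicion, and the oncology route picks up those not already identified, so the cohort-wide shift is diluted. Eligibility requires expected survival beyond 3 months, so early deaths are probably fewer than a constant hazard implies. Nothing in the documents shows that recruitment route is related to sarcopenia.

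A reader might infer that the survival results are biased outright, or that the non-cancer comparison cannot be computed. The documents support neither. Non-cancer participants have consented and been tested at baseline, so a comparison is possible once a start date is named, and survival is only one variable in a secondary comparison.

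A reader might also infer that baseline should be time zero for everyone. That only moves the problem: a patient enrolled on suspicion is classed as having cancer only on surviving to diagnosis, so the time from baseline to diagnosis would be guaranteed survival.

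What the reply does not remove is that the one clock the protocol states does not fit its two entry points and cannot supply a comparison planned in the same section.

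**Conclusion.** The point holds in a limited form. Followed as written, the protocol credits post-diagnosis entrants with time in which they could not have died, and it leaves the cancer versus non-cancer survival comparison without a defined start. The first defect raises apparent 1-year survival in that route by roughly 1 to 6 percentage points, assuming delays of 2 to 8 weeks, true survival of 40% to 60% and a constant hazard. It is less across the cohort, in proportion to the share entering after diagnosis. The sarcopenia hazard ratio, on which the sample size rests, is little affected unless delay is related to sarcopenia. The second defect rests on no assumption. No sample-size figure changes.

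**What to change.** - **Lung cancer patients:** start time at risk at the later of the baseline assessment and the diagnosis date. Use that date as time zero or, if survival is to be reported from diagnosis, as the delayed-entry time.
- **Cancer versus non-cancer:** use one origin available to both groups, namely the date the diagnostic work-up was resolved or, if later, the baseline assessment. For cancer patients, the work-up is resolved at diagnosis, so the two rules agree.
- **Extraction:** in section 7.1, run the record review to 1 and 5 years from the chosen origin and say that it covers non-cancer participants. Add the same origin to Table 1.

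The cost is slightly more analysis work and a slightly longer extraction window for some patients. Baseline testing is done on everyone compared, and time since diagnosis is already collected. The date on which cancer was ruled out is not among the items listed in section 7.1 and would have to be taken from the record.
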